	
(according to local countries clinical practice guidance) as maintenance therapy. All patients will receive a loading dose of clopidogrel (600 mg) if not already on maintenance dose either before PCI or otherwise at the time of PCI, and then maintain a maintenance dose of 75 mg/day. If the local clinical guidance recommends use of Ticagrelor or Prasugrel, the recommended doses will be: Either before PCI or otherwise at the time of PCI, all patients will receive a loading dose of Ticagrelor 180 mg if not already on a maintenance dose, and then stay on a maintenance dose of 90 mg twice daily. Or either before PCI or otherwise at the time of PCI, all patients will receive a loading dose of Prasugrel 60 mg if not already on a maintenance dose, and then stay on a maintenance dose of 5-10 mg daily.
 
Patients with symptoms of ACS due to NSTEMI who are being triaged in the Emergency Room/hospital and who are selected for early PCI will be screened for the study. Enrollment should occur once the patient has completed screening and satisfied all the I/E criteria. Initiation of the MT1002 intravenous injection would then only start just before the PCI procedure. All patients will be given routine care for ACS according to applicable guidelines including analgesics, nitrates, beta-blockers, and potentially additional drugs as needed (anti-arrhythmic drugs, statins, angiotensin-converting enzyme inhibitors/angiotensin II receptor blockers, calcium-channel blockers, proton pump inhibitors, etc.).
 
If a patient meets all the admission criteria and all the eligibility criteria, he/she can be enrolled to MT1002 (1 of 3 dose levels) and undergo early PCI (including diagnostic coronary angiography procedure).
 
Procedure: either radial access/distal radial access PCI or femoral access PCI will be used in this study. It is up to the discretion of the Principal Investigator what type of stent(s), if indicated, will be used.
 
Follow-up: At completion of PCI, subjects will be continued on IV MT1002 for 4 hours from infusion start. All patients will stay on clopidogrel 75 mg/day. If the local clinical guidance recommends use of Ticagrelor or Prasugrel, the recommended maintenance doses will be: Ticagrelor 90 mg twice daily or Prasugrel 5-10 mg daily and aspirin 75-100 mg/day (according to local countries clinical practice guidance) and be followed up for 30 days. Longer-term follow-on treatment will be done according to local treatment guidelines outside of this protocol.
 
Rescue: Patients who fail to achieve an ACT target of 200 to 300 sec with MT1002 (within 30 minutes after MT1002 infusion initiation) will be switched to standard of care (unfractionated heparin or bivalirudin) and discontinued from the study drug.

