
• Bolus dosing All patients will receive 0.75 mg/kg as an IV bolus dose, followed immediately by 1.6 mg/kg/hr*4h IV for the duration of the PCI. Five minutes after the bolus dose, ACT should be performed and an additional bolus of 0.3 mg/kg IV may be given if needed (i.e., ACT <200 sec).									

• Dosing during infusion period 10 minutes after initiation of 1.6 mg/kg/hr IV for the duration of the PCI, or 5 minutes after additional bolus if it is given, additional ACT can be monitored, and IP infusion rate can be adjusted. An incremental 10% additional infusion rate can be titrated up until ACT >200 sec. If ACT >300 sec during that period of time, IP infusion can be stopped for 5 minutes, and/or the rate of infusion can be adjusted until ACT maintains between 200 sec and 300 sec. Duration of IP infusion can be 4 hours +-30 minutes in order to accommodate potential infusion rate adjustments.									

Reference Therapy:	None
Treatment Duration:	Treatment in preparation for PCI, during PCI, and until approximately 4 hours after enrollment. Patients will receive MT1002 IV followed by MT1002 infusion for 4 hours. This regimen was found safe and well tolerated in Phase 1. MT1002 will be initiated as close to the start of PCI as possible. PCI can start after MT1002 initiation as soon as ACT is confirmed to be ≥ 200 sec or within 30 min after MT1002 starts, whichever occurs first. Patients will be discharged from the hospital when they are stable, as defined by the Investigator's judgment. Patients will be followed for 30 days from study drug dosing.
Key Efficacy:	The numbers of patients who achieve ACT target 200 to 300 sec, and measurement of Platelet Aggregation (PA)
Key Safety:	General safety (including vital signs, physical examination, electrocardiogram [ECG], laboratory assessments), AEs, MACE within 30 days, and major bleeding events
Pharmacokinetics:	PK levels of MT1002
Pharmacodynamics:	ACT, aPTT, PT, TT, FIB, INR
Other Assessments:	Thrombolysis in myocardial infarction (TIMI) flow assessments; creatine kinase (CK)-MB, and troponin I (troponin T can be measured if the local site does not have the troponin I test)

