In $\leq 1/6$ pat lab values preventing dose escalation such as LFT up by $\geq 2 \times$ from baseline; platelet count < 50,000; QTcF interval > 500 ms or > 60 ms change from baseline, based on ECGs; or study drug related vital sign changes that require stabilization of hemodynamics with positive inotropes	Lab values preventing dose continuation such as LFT up by $\geq 2 \times$ from baseline; platelet count < 50,000; QTcF interval > 500 ms or > 60 ms change from baseline, based on ECGs; or study drug related vital sign changes that require stabilization of hemodynamics with positive inotropes	In $\geq 2/6$ pat lab value preventing dose escalation such as LFT up by $\geq 2 \times$ from baseline; platelet count < 50,000; QTcF interval > 500 ms or > 60 ms change from baseline, based on ECGs; or study drug related vital sign changes that require stabilization of hemodynamics with positive inotropes	In $\leq 1/6$ pat lab values preventing dose escalation such as LFT up by $\geq 2 \times$ from baseline; platelet count < 50,000; QTcF interval > 500 ms or > 60 ms change from baseline, based on ECGs; or study drug related vital sign changes that require stabilization of hemodynamics with positive inotropes	In $\geq 3/6$ pat lab values preventing dose escalation such as LFT up by $\geq 2 \times$ from baseline; platelet count < 50,000; QTcF interval > 500 ms or > 60 ms change from baseline, based on ECGs; or study drug related vital sign changes that require stabilization of hemodynamics with positive inotropes

Abbreviations: AE, adverse event; ACT, activated clotting time; BARC, Bleeding Academic Research Consortium; ECG, electrocardiogram; LFT, liver function test; pat, patient; QTcF, QT interval corrected by Fridericia's formula; SAE, serious AE.

The decision on dose escalation/de-escalation/stopping or continuation for the patient cohort will be taken by the Study Management Group based on data review of each dose group considering safety, efficacy, drug concentration, and in conjunction with the prespecified criteria.

End of Cohort 1 SMG meeting held on March 23, 2023 recommended to proceed to cohort 3 if patients in cohort 2 shows insufficient anticoagulation effect. Insufficient anticoagulation effect is defined when 3 patients or more treated within cohort 2 dosing regimen experienced at least one ACT<200 seconds and confirmed by Ad Hoc SMG meeting.

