Follow-up: At completion of PCI, subjects will be continued on IV MT1002 for 4 hours from infusion start. All patients will stay on clopidogrel 75 mg/day. If the local clinical guidance recommends use of Ticagrelor or Prasugrel, the recommended maintenance doses will be: Ticagrelor 90 mg twice daily or Prasugrel 5-10 mg daily and aspirin 75-100 mg/day (according to local countries clinical practice guidance) and be followed up for 30 days. Longer-term follow-on treatment will be done according to local treatment guidelines outside of this protocol.

Rescue: Patients who fail to achieve an ACT target of 200 to 300 sec with MT1002 (within 30 minutes after MT1002 infusion initiation) will be switched to standard of care (unfractionated heparin [UFH] or bivalirudin) and discontinued from the study drug.

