8.2 Dosage Schedule

Patients will receive MT1002 IV followed by MT1002 infusion for 4 hours. This regimen was found safe and well tolerated in Phase 1. MT1002 will be initiated as close to the start of PCI as possible. MT1002 should be initiated during diagnostics angiography when indication for PCI is confirmed, provided the early PCI is indicated right after the coronary angiography. PCI can start after MT1002 initiation as soon as ACT is confirmed to be ≥ 200 sec or within 30 min after MT1002 starts, whichever occurs first. MT1002 will be administered by an intravenous injection of 0.90 mg/kg, 1.2 mg/kg, 0.75 mg/kg or 0.6 mg/kg (depending on the dose selected for the cohort) via IV access prior to the PCI procedure, immediately followed by an IV infusion of 1.8 mg/kg/hour, 2.3 mg/kg/hour, 1.6 mg/kg/hour or 1.2 mg/kg/hour (depending on the dose selected for the cohort) until completion of the procedure.

Patients will be discharged from the hospital when they are stable, as defined by the Investigator's judgment. Patients will be followed for 30 days from study drug dosing.

Three doses of MT1002 will be evaluated in this study as noted in the table below. The first dose level is 0.90 mg/kg initial loading dose (bolus intravenous injection) + 1.8 mg/kg/h (infusion) for 4 hours. The second dose level will be based on the results from the first cohort (If the dose is escalated, then the second dose level is 1.2 mg/kg initial loading dose (bolus intravenous injection) + 2.3 mg/kg/h (infusion) for 4 hours; if the dose is de-escalated, then the second dose level is 0.6 mg/kg initial loading dose (bolus intravenous injection) + 1.2 mg/kg/h (infusion) for 4 hours). The third dose will be based on the results from the initial 2 cohorts (Table 3). The goal is to achieve a target ACT of 200 to 300 sec (within 30 minutes after infusion initiation) during the continuous infusion period of MT1002.

Patients who are enrolled but do not undergo PCI (e.g., because of PCI contraindication revealed after coronary angiography or due to exclusion criteria) will be replaced for the study. However, the patients will be evaluated as safety population.

Dose adjustment guideline for cohort 3 dosing regimen is below. All adjustment will be documented in the patient's source document in detail:

- Bolus and maintenance dosing

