All patients will receive 0.75 mg/kg as an IV bolus dose, followed immediately by 1.6 mg/kg/hr*4h IV for the duration of the PCI. Five minutes after the bolus dose, ACT should be performed and an additional bolus of 0.3 mg/kg IV may be given if needed (i.e., ACT <200 sec).

- Dosing during infusion period

10 minutes after initiation of 1.6 mg/kg/hr IV for the duration of the PCI, or 5 minutes after additional bolus if it is given, additional ACT can be monitored, and IP infusion rate can be adjusted. An incremental 10% additional infusion rate can be titrated up until ACT >200 sec. If ACT >300 sec during that period of time, IP infusion can be stopped for 5 minutes, and/or the rate of infusion can be adjusted until ACT maintains between 200 sec and 300 sec. Duration of IP infusion can be 4 hours +/-30 minutes in order to accommodate potential infusion rate adjustments.

Table 3 Planned Dose Regimen of MT1002 for Injection and Expected ACT and aPTT Values

Sequence	N	MT1002: Initial loading dose and maintenance dose	Expected peak ACT based on Phase 1 results in healthy volunteers	Expected peak aPTT based on Phase 1 results in healthy volunteers	Expected ACT in 5 min after MT1002 start	Expected aPTT in 5 min after MT1002 start	Expected ACT in 30 min after MT1002 start	Expected aPTT in 30 min after MT1002 start
First dose cohort	6	0.90 mg/kg + 1.8 mg/kg/h*4h	234.3±26.1 sec – at 4 hours	74.4±6.2 sec – at 4 hours	209.7±19.2	63±4.8	212.3±29.5	65.6±7.5
Second cohort if dose escalated	6	1.2 mg/kg + 2.3mg/kg/h*4h	253.8±9.6 sec – at 2 hours	83.6±5.4 sec – at 4 hours	234.3±6.9	74.5±7.3	240.3±4.1	78.3±9
Second cohort if dose de-escalated	6	0.60 mg/kg + 1.2 mg/kg/h*4h	221.7±11.1 sec – at 2 hours	65.9±2.5 sec – at 4 hours	194.5±28.6	56.5±7.4	216.2±15.7	60.6±4.4
Third expansion cohort	6-8	0.75 mg/kg + 1.6 mg/kg/h*4h based on results from initial 2 cohorts	220.7 sec at 4 hours	67.7 sec at 4 hours	217.5	66.5	216.5	66.1

Abbreviations: ACT, activated clotting time; aPTT, activated partial thromboplastin time; h, hours; min, minutes; N, number of patients; sec, seconds; Tbd, to be determined.

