- Administer study drug via IV access before the PCI and record time of dosing in the eCRF. Study drug should be administered in catheterization lab as close to randomization and the start of the PCI procedure as possible.
- Conduct a visual bleeding inspection and assess bleeding AEs according to the BARC criteria; record any patient-reported bleeding.
- Record any other AEs that have occurred.

9.2.3 During Percutaneous Coronary Intervention, Day 1

Either radial access/distal radial access PCI or femoral access PCI will be used in this study. It is up to the discretion of the Principal Investigator what type of stent(s) will be used.

- Conduct the PCI procedure per local standard of care.
- Record TIMI flow grade post PCI.
- Patients who fail to achieve ACT target of 200 to 300 sec with MT1002 (within 30 minutes after MT1002 infusion initiation) before PCI will be switched to standard of care (UFH or bivalirudin, see Section 8.5.1).
- Patients who achieve ACT target of 200 to 300 sec with MT1002 (within 30 minutes after MT1002 infusion initiation) before PCI should continue the study drug infusion for 4 ± 0.5 hours after infusion start.
- Monitor patients for potential AEs, including allergic reactions during the MT1002 administration.
- Record vital signs (body temperature, respiration rate, heart rate, and systolic and diastolic blood pressure).
- Record any procedural complications, as well as any other AEs
 - Glycoprotein IIb/IIIa inhibitors may be used for procedural or angiographic complications only (dosing per local standard of care, see Section 8.5.1)
 - In those patients who experience significant intracoronary thrombosis during the procedure, or experience acute thrombosis after the procedure, heparin bail out may be administered (see Section 8.5.1).
- Perform a PA (by PFA100 or PFA200) according to the time points in the Schedule of Assessments (Table 4) and Table 5.

- Obtain central cardiac biomarkers (troponin I [troponin T can be measured if the local site does not have the troponin I test], and CK-MB) according to the time points in the Schedule of Assessments (Table 4) and Table 5.
- Obtain coagulogram (ACT, aPTT, PT, TT, FIB, INR according to the time points in the Schedule of Assessments [Table 4] and Table 5), hemoglobin, hematocrit, platelet count, RBC, and WBC counts.
- Obtain PK samples according to the time points in the Schedule of Assessments (Table 4) and Table 5.

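### The rescue rule is two-sided as written, so a patient whose ACT stays above 300 sec through 30 minutes must be switched to another anticoagulant; limit it to patients who have not reached 200 sec

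*Combined protocol and SAP*

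**What the plan says.** **Rescue.** Section 6.1 (Rescue paragraph) covers "Patients who fail to achieve an ACT target of 200 to 300 sec with MT1002", judged within 30 minutes of starting the infusion. The synopsis gives the action: such patients "will be switched to standard of care (unfractionated heparin or bivalirudin) and discontinued from the study drug". Section 9.2.3 repeats the two-bounded target and says that patients who miss it "before PCI will be switched to standard of care (UFH or bivalirudin, see Section 8.5.1"). Its next bullet says that patients who reach the same range "before PCI should continue the study drug infusion". Section 8.5.1 repeats the range for both UFH and bivalirudin in permissive wording. It requires MT1002 to be off for 30 minutes (at least 30 for bivalirudin) before either agent.

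**High ACT elsewhere.** The Cohort 3 guideline in Section 8.2 says "If ACT >300 sec during that period of time, IP infusion can be stopped for 5 minutes", and the synopsis version adds that "the rate of infusion can be adjusted until ACT maintains between 200 sec and 300 sec". In Table 1 (Section 6.1, also in the synopsis), an ACT above 350 sec in an individual patient is a reason to stop the infusion temporarily.

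**Low ACT elsewhere.** Section 8.2 says "PCI can start after MT1002 initiation as soon as ACT is confirmed to be" at least 200 sec, or within 30 minutes, whichever is first. Section 6.1 says "Insufficient anticoagulation effect is defined when 3 patients or more treated within cohort 2 dosing regimen experienced at least one ACT<200 seconds".

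**Endpoint.** The first co-primary (Section 5.2.1) counts patients with ACT of 200 to 300 sec on MT1002, with no switch to standard of care, and with PCI success.

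**The concern.** A range can be missed on either side. Low ACT calls for an effective anticoagulant, and a switch is sensible. ACT held above 300 sec means too much effect from a short-acting infusion that can be paused or slowed. The rescue sentence treats both alike: MT1002 ends and another anticoagulant follows.

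Two things are at stake. The first is the instruction to sites. An investigator who sensibly pauses the infusion in such a patient and resumes it departs from the protocol, and sites may differ in what they do. The second is the reading of the co-primary. A forced switch is a failure on that endpoint whatever its cause, so overshoot and lack of effect would be counted together. In a dose-finding trial they point to opposite dose changes.

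**Working it through.** The plan gives no figure for this rule, so the check compares texts and then asks whether the high side can be reached.

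**1. Who meets the literal trigger.** The trigger is no ACT in 200 to 300 sec within 30 minutes. Table 5 schedules ACT at 5 minutes and 0.5 hours after dose initiation.

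| Course to 30 minutes | In range by 30 min? | Literal rescue? |
|---|---|---|
| Never reaches 200 sec | No | Yes, sensible |
| Above 300 sec, then brought into range | Yes | No |
| In range, then above 300 or below 200 sec | Yes | No |
| Above 300 sec at every reading | No | Yes, wrong action |

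Only the last row is at issue.

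**2. What other rules say about that row.** Above 350 sec, Table 1 prescribes a temporary stop, whereas rescue is permanent. In Cohort 3, Section 8.2 allows ACT monitoring from 10 minutes into the infusion and then a pause or rate change. Adjustment can therefore come before the 30-minute check, and the conflict is confined to overshoot that persists despite it. At 301 to 350 sec in a fixed-dose cohort, no individual rule other than rescue applies.

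**3. Is it reachable?** The Version 6.0 entry in the amendment history reports for Cohort 1 (0.90 mg/kg bolus, 6 patients):
- 3 patients above 300 sec at 5 minutes;
- 1 patient above 300 sec at 30 minutes;
- overlap between these not stated;
- target ACT achieved, with successful PCI, in all 6.

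The two early counts alone would allow 0 or 1 patient to meet the trigger. The report of target ACT in all 6 favours 0. Exact (Clopper-Pearson) 95% intervals are 0 to 45.9% for 0/6 and 0.4 to 64.1% for 1/6; the second describes ACT above 300 sec at 30 minutes, not the trigger itself.

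Healthy-volunteer values from Table 3 for the same dose, assuming normality:
- 30 minutes, 212.3 ± 29.5: z = (300 − 212.3)/29.5 = 2.97, P(ACT > 300) = 0.15%.
- At least 1 of 6: 1 − (1 − 0.001475)^6 = 0.9%.
- 5 minutes, 209.7 ± 19.2: z = (300 − 209.7)/19.2 = 4.70, P = 0.00013%.

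Cohort 1 showed 1/6 and 3/6, so patients ran above the volunteer values. Those values cannot be used to dismiss the high side. Tail areas this far out, from Phase 1 groups of 6, carry no more weight than that.

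**4. Effect of a one-sided threshold on low-side rescue.** From Table 3 at 30 minutes, assuming normality:
- 0.60 mg/kg: z = (200 − 216.2)/15.7 = −1.03, P(ACT < 200) = 15.1%.
- 0.90 mg/kg: z = (200 − 212.3)/29.5 = −0.42, P(ACT < 200) = 33.8%.

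The wording matters. Some patients would be at 200 sec or more at 5 minutes and below 200 at 30 minutes. With an assumed correlation between the two readings of 0.8 down to 0, their share is 0.2% to 6.4% at 0.60 mg/kg (5-minute value 194.5 ± 28.6) and 10.8% to 23.5% at 0.90 mg/kg. At correlation 0 this is 0.424 × 0.151 = 6.4% and 0.693 × 0.338 = 23.5%. A trigger of ACT below 200 at 30 minutes would switch these patients, most of whom the present rule keeps on MT1002. A trigger of not having reached 200 within 30 minutes does not.

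**The case against.** The strongest reply is that the plan intends a sequence: adjust first, and switch only if ACT is still out of range at 30 minutes. Section 8.2 states its ACT goal with that same 30-minute limit, and the Cohort 3 guideline is permissive. This stands in large part. A reader might infer that the rescue rule flatly contradicts the Cohort 3 guideline; the text supports a conflict only for overshoot that persists despite adjustment.

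Second, the PCI start threshold and the definition of insufficient effect are low-side by design. A reader might cite them as proof that high ACT is acceptable. They do not show that, and Table 1 counts peak ACT above 300 sec toward de-escalation. They add little here. Nor is the permissive wording in Section 8.5.1 a contradiction; it repeats the same range.

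Third, a patient above 300 sec passes the PCI threshold at once and may already be in PCI, arguably outside the before-PCI wording of Section 9.2.3. That stands for 9.2.3, but the synopsis and 6.1 carry no such limit.

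Fourth, the word rescue suggests low-side intent that clinicians would recognise. Probably so, but the text makes the switch mandatory on both sides.

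Fifth, withdrawing a patient who stays out of range on a fixed dose is a defensible stopping rule. Stopping MT1002 may be; requiring another anticoagulant because ACT is too high is not. This reply does tell against writing a new pause or rate-reduction rule for the fixed-dose cohort, since that would alter the ACT and PK data used for dose decisions.

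**Conclusion.** The point holds in a narrow form. The synopsis, 6.1 and 9.2.3 make the switch mandatory for a patient whose ACT has stayed above 300 sec with no in-range value within 30 minutes. That is the wrong action for excess anticoagulation, and it disagrees with the Table 1 temporary stop above 350 sec and with the Cohort 3 guideline when overshoot persists.

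It is a minor to moderate safety wording correction. Two stronger readings are tempting and not supported. One is that a Cohort 1 patient should have been switched, making the co-primary count 5/6; the protocol reports target ACT in all 6, and no patient is shown to have met the trigger. The other is that the rule stacks two anticoagulants; Section 8.5.1 requires 30 minutes off MT1002 first.

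The remaining starting doses (0.60 and 0.75 mg/kg) are below the 0.90 mg/kg of Cohort 1, which makes the case less likely. In Cohort 3 the optional extra bolus can take the total to 0.75 + 0.30 = 1.05 mg/kg, but only after an ACT below 200 sec.

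The conclusion rests on the literal text and on a clinical judgement about high ACT. It does not depend on the normality or correlation assumptions, which bear only on reachability and on the choice of wording.

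**What to change.** In the synopsis, 6.1 and 9.2.3, replace the trigger with wording such as:

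> Rescue applies to patients who have not reached ACT ≥ 200 sec within 30 minutes after MT1002 infusion initiation (in Cohort 3, after any additional bolus and titration). They are switched to UFH or bivalirudin and stop study drug. ACT > 300 sec alone is not a reason to switch; it is managed by the existing rules (Cohort 3 dose adjustment guideline; Table 1 temporary stop above 350 sec).

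Use the same threshold in both Section 8.5.1 entries, which may stay permissive, and make the continuation bullet in 9.2.3 match (ACT ≥ 200 sec reached). Keep the 200 to 300 sec co-primary definition in 5.2.1. Report patients persistently above 300 sec on a separate line from those who never reached 200 sec. Do not add a new pause or rate-reduction rule for the fixed-dose cohort.

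**Cost.** One passage in three places, one threshold in 8.5.1, one bullet and one table line. The sample size and the cohort decision rules do not change. The downside is that a patient with persistent ACT of 301 to 350 sec in a fixed-dose cohort stays on MT1002 under investigator judgement.
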